## 1 BACKGROUND

Medical termination of intrauterine pregnancy, also known as medication abortion, is a safe and effective alternative to surgical abortion (vacuum aspiration). Mifeprex® (generic: mifepristone), a progestin antagonist that competitively interacts with progesterone at progesterone- receptor sites, used together with misoprostol is the gold standard regimen for medication abortion. In studies performed in the United States up to 70 days gestation using this dosing regimen, 97.4% of patients reportedly had a complete abortion (FDA 2016). Another 2.6% received surgical intervention, or vacuum aspiration, for reasons such as ongoing pregnancy, patient request, bleeding, medical necessity and incomplete expulsion.

Medication abortion up to 70 days gestation with mifepristone 200 mg orally followed by misoprostol 800 mcg administered via the buccal or vaginal route has a favorable safety profile. Although serious and sometimes fatal infections have been reported with this treatment, this complication is very rare; only 8 deaths related to sepsis have been reported among almost 3 million uses of the medication (FDA 2011). Uterine bleeding requiring medical or surgical intervention is also a known complication of the treatment. Heavy bleeding requiring surgical treatment occurs in approximately 1% of patients, and blood transfusion is required in <0.1%. Adverse events that are more common include nausea, vomiting, weakness, fever/chills, headache, diarrhea and dizziness (FDA 2016).

In March 2016, the Food and Drug Administration (FDA) approved an updated label for Mifeprex® to reflect recent research published since the drug's original approval in 2000 (FDA 2016). The approved dosing regimen includes oral mifepristone (200 mg) followed by a dose of misoprostol (800 mcg) administered buccally 24-48 hours later. The changes made to the label included a more effective dosing regimen containing less mifepristone (200 mg instead of 600 mg) and more misoprostol (800 mcg instead of 400 mcg) via the buccal route, extension of the gestational age limit for treatment from 49 to 70 days, removal of the recommendation for in- person follow-up, removal of language indicating that the prescriber must be a physician, and elimination of the requirement to report nonfatal adverse events to Danco Laboratories, LLC, the drug's US distributor, and the FDA.

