### **10.3 Clinical follow-up**

Women undergoing medication abortion generally undergo clinical follow-up to ensure that the abortion is complete. Follow up to ensure no ongoing pregnancy at approximately 7-14 days after the initial visit may be completed in one of three ways: 1) an in-person clinic visit with ultrasound, 2) an in-person clinic visit with serum hCG (in the case that serum hCG was measured on the day the Mifeprex® was prescribed; the follow-up laboratory test may be performed at an off-site laboratory), or 3) a telephone follow-up with the clinic at approximately 1 week after Mifeprex® was taken, followed by a urine pregnancy test at 3-4 weeks (at home) post medication abortion. Results from these measures will be documented in the clinical record and later abstracted for data collection. No study-related activities will be performed as part of this clinical follow-up. Participants with ongoing pregnancy will be managed according to the standard practice at the site, and may include an additional dose of misoprostol, repeating Mifeprex® and misoprostol, or vacuum aspiration. Those who need additional medications will receive either a prescription or referral to another facility. If the participant is referred to another facility for a vacuum aspiration or other treatment related to the medication abortion or if the participant spontaneously goes to another facility, the site PI or delegate will contact the referral site to document the treatment given, abortion outcome (if relevant), and any AEs or SAEs. No study activities will take place at follow-up clinical visits, although clinical information recorded at these visits will be later abstracted from the patient's record (see section 9.1).

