### **10.5 Data Abstraction**

As noted above in section 9, de-identified data about the clinical visits of participants consenting for the study will be abstracted from the electronic medical record system of the participating sites. This includes clinical information including demographics (age, parity, race, ethnicity), initial visit information (date of service, gestational age, past medical history, medications, laboratory values), and follow-up visit information (date(s) of service, treatment given, symptoms, outcome of abortion, adverse events, and other follow-up care). The site PI will perform a chart review for each participant 6 weeks

after enrollment. De-identified data will be entered into a REDCap electronic form. As noted above, the site PI will supervise the data abstraction and replace the participant name with the Study ID prior to transferring the data to the UCSF research team.

The study team will request consent from participants to obtain access to medical record data related to the abortion, pregnancy, and subsequent birth (if relevant) including through records' release from other facilities. This will enable the study team to collect data on visits to other medical facilities and on pregnancy outcomes for participants.

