## 16.4 Analysis of Secondary Endpoints

Feasibility of the mail-order pharmacy dispensing model will be assessed through surveys with patients, and include determination of the proportion of patients who receive the medications by Day 2 and by Day 3 after the prescription is sent, the quality of the packaging, whether patient confidentiality was compromised due to receiving the medications by mail, as well as the proportion of patients who had to go to the clinic to obtain the medications.

Clinical effectiveness and safety outcomes, including adverse events, with medication abortion obtained via mail-order pharmacy will be assessed using quantitative data abstracted from patient medical records, as well as information on clinical outcomes captured in the Day 14 patient survey. The analysis populations for the effectiveness and safety endpoints will include patients who enroll in the study, take either of the medications, and for whom we have follow-up data. We will not assume that patients who do not have follow-up data had a successful abortion.

Effectiveness will be defined as the successful completion of abortion (versus incomplete abortion or continuing pregnancy), without vacuum aspiration. Continuing pregnancy will be defined as a viable pregnancy following treatment and need for vacuum aspiration to terminate the pregnancy or cases where a patient elects to continue the pregnancy after failed treatment (Creinin & Chen 2016). We will document vacuum aspiration abortions, including reasons for aspiration, reported by participants and those determined as necessary by the study providers at follow-up visits. We will compare effectiveness (the proportion of our sample that experiences a complete abortion not requiring vacuum aspiration) with published estimates (97.4%) (FDA 2016), using an exact binomial test. Assuming 10% loss to follow-up and 10% adjustment for clustering, and a two-sided alpha of 0.025 (to account for type I error), we estimate that a final analytic sample ranging from approximately 400 to 560 patients gives us 98% to 100% power to determine that mail-order medication abortion is as effective as in-person dispensing, if effectiveness in the mail-order model is no lower than 92.4%. A non-inferiority limit is defined as -5% and as an acceptable difference in the proportion of complete abortions.

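### A viable pregnancy after the mailed course that is ended with further medication is not counted as a continuing pregnancy and, once complete, meets the definition of success

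*Combined protocol and SAP*

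**What the plan says.** Section 16.4 defines the endpoint: "Effectiveness will be defined as the successful completion of abortion (versus incomplete abortion or continuing pregnancy), without vacuum aspiration". The quantity compared with the published 97.4% is "the proportion of our sample that experiences a complete abortion not requiring vacuum aspiration". Continuing pregnancy has two limbs. The first is: "Continuing pregnancy will be defined as a viable pregnancy following treatment and need for vacuum aspiration to terminate the pregnancy". The second is: "or cases where a patient elects to continue the pregnancy after failed treatment". Neither limb mentions further medication, and incomplete abortion is not defined.

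Section 10.3 says that ongoing pregnancy is handled by each site's usual practice, which "may include an additional dose of misoprostol, repeating Mifeprex® and misoprostol, or vacuum aspiration". On supply it says: "Those who need additional medications will receive either a prescription or referral to another facility".

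Section 1 describes the failures behind the benchmark this way: "Another 2.6% received surgical intervention, or vacuum aspiration, for reasons such as ongoing pregnancy", along with other reasons. Section 10.5 lists what is abstracted from follow-up visits, including "treatment given, symptoms, outcome of abortion, adverse events, and other follow-up care".

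**The concern.** Sections 2 and 3.3 say that the only thing changed in this study is how the drug is dispensed. The first mailed course is therefore what a reader wants to know about. Under Section 16.4, a first course that left a viable pregnancy can drop out of the continuing-pregnancy count and enter the success count because of a later course, which may have come by a new prescription or from another facility.

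Two things are at stake. First, the continuing-pregnancy figure would not count every pregnancy that survived the mailed course. Second, the study plans 15 to 20 sites that follow local practice. The same first-course result would be a failure at a site that aspirates and a success at one that re-medicates, so both figures depend partly on site habit.

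**Working it through.** **Step 1. The plan's own power figure.** Inputs from Section 16.4: expected success 97.4%; limit 97.4% − 5 points = 92.4%; two-sided alpha 0.025, so 0.0125 in the tested tail; 400 to 560 analysed; 10% adjustment for clustering (400/1.1 = 364; 560/1.1 = 509). Rule: the smallest r with P(X ≥ r | n, 0.924) ≤ 0.0125. Power = P(X ≥ r | n, 0.974), exact binomial.

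| n | r needed | failures allowed | actual tail | power |
|---|---|---|---|---|
| 364 | 348 | 16 | 0.0095 | 98.4% |
| 400 | 382 | 18 | 0.0087 | 99.0% |
| 509 | 484 | 25 | 0.0103 | 99.9% |
| 560 | 532 | 28 | 0.0094 | 99.95% |

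The stated 98% to 100% reproduces. The point is one of definition, not arithmetic.

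**Step 2. Applying the definitions.** Take a patient with a viable pregnancy after the first mailed course.

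| What happens next | Continuing pregnancy (16.4)? | Success (16.4)? |
|---|---|---|
| Aspiration | Yes, first limb | No |
| She chooses to continue | Yes, second limb | No |
| More misoprostol, then complete, no aspiration | Neither limb | Yes |
| Second course of both drugs, then complete, no aspiration | Neither limb | Yes |

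Rows three and four are routes that Section 10.3 provides for. Nothing in the documents counts them as failures, reports them separately or limits success to the first course.

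**Step 3. Size.** Let q be the share of analysed patients in rows three and four. The documents give no value, so 0% to 2% is an assumption. Patients reclassified = n × q. First-course success = reported success − q. The last column supposes that reported success is 97.4%.

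| q | of 400 | of 560 | first-course success |
|---|---|---|---|
| 0% | 0 | 0 | 97.4% |
| 0.5% | 2 | 2.8 | 96.9% |
| 1% | 4 | 5.6 | 96.4% |
| 2% | 8 | 11.2 | 95.4% |

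**Step 4. What a second non-inferiority test would cost.** If first-course success were also tested against 92.4%, power at n = 400 would go from 99.0% to 95.4%, 86.3% and 52.4% for q = 0.5%, 1% and 2%. At n = 560 it would go from 99.95% to 99.4%, 96.5% and 71.7%. This bears on the choice of fix.

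**The case against.** The strongest reply is that the benchmark uses the same yardstick. Section 1 describes the 2.6% who make up the remainder of 97.4% as having had surgical intervention. If 97.4%, and hence 92.4%, rests on a no-aspiration definition, the tested endpoint matches it. This stands for the comparison with 97.4%. It does not help the continuing-pregnancy count or the absolute success of the first mailed course.

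A reader might go further and infer that the non-inferiority test is too lenient. Suppose first-course success is exactly 92.4% and q is added as successes. The chance of declaring non-inferiority at n = 400 then rises from 0.9% to 2.2%, 5.0% and 20.1% for q = 0.5%, 1% and 2%. The arithmetic is right, but it sets a first-course rate against a limit that may be defined by absence of aspiration. If the limit is so defined, the error at the limit stays at 0.9%. The documents do not say whether the benchmark studies allowed or excluded repeat medication, so they do not support the inference. The upper end of q is also large beside the benchmark: 1% to 2% would be 38% to 77% of the 2.6% surgical total for all reasons (1/2.6 and 2/2.6).

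Other replies stand in part. The plan never says in words that re-medicated patients are successes; that follows from reading Sections 16.4 and 10.3 together. Section 16.4 cites a published reporting guideline for its definition, and agreement with that guideline cannot be checked from the documents. Effectiveness is a secondary outcome, and no test is planned on continuing pregnancy. Section 16 promises a detailed SAP before the final analysis. These replies lower the importance of the point, but none tells an abstractor how to code these patients.

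**Conclusion.** The gap is real. As written, continuing pregnancy is undercounted whenever a viable pregnancy is ended with further medication. First-course success is then overstated by exactly q, and is never understated. Classification depends on site practice. The direction follows from the definitions. The size is unknown: 0 to 8 of 400 patients at an assumed q of 0% to 2%.

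No bias is claimed in the comparison with 97.4%, which may be like for like, and the stated power is sound for the endpoint as defined. This is a cheap improvement to a secondary outcome, not a threat to the study's main conclusion.

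**What to change.** Amend Section 16.4, or settle it in the SAP that Section 16 promises:

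- **Comparison with 97.4%.** Keep completion with no aspiration as the endpoint, stated on its own. At present Section 16.4 defines effectiveness by contrast with continuing pregnancy, so widening that term without separating the two would change the tested endpoint as well.
- **Separate outcome.** Report any viable pregnancy after the first mailed course, whatever followed, broken down by management: additional misoprostol alone, repeat Mifeprex and misoprostol, aspiration, or pregnancy continued.
- **Sensitivity estimate.** Pre-specify success after the first mailed course alone, with a confidence interval, counting viable pregnancies given any repeat abortion medication as failures.

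Do not require non-inferiority under both definitions. The 92.4% limit may not apply to first-course success, and Step 4 shows the loss of power could be large.

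The cost is one more table, and first-course effectiveness may look slightly lower than the headline figure. Treatment given and outcome are already abstracted under Section 10.5, so no new data are needed. Clinical management is unchanged.

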EFFICACY EVALUATIONS	The UCSF study team will train sites on standardized recruitment and consent procedures and have regular communication with study clinics to provide technical assistance and check on progress of study.  Data collection tools and procedures will be pilot tested before implementation. Data will also be monitored periodically to ensure that data collection, coding, and management procedures are being conducted according to protocol and ethical guidelines.
PRIMARY ENDPOINT	The primary outcome will be acceptability of undergoing medication abortion with drugs dispensed by mail-order pharmacy, measured by the proportion of patients reporting they would use the mail-order service again if they needed another abortion, as well as the proportion who report they were “satisfied or very satisfied” with the medication abortion. We will also capture patient perspectives on receiving the medications by mail through open-ended responses. In addition, we will ask patients who decline to enroll in the study their reasons, including the reasons why they are not interested in receiving the medications by mail.

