### 16.3 Analysis of Primary Endpoint

Acceptability and satisfaction with the mail-order model among patients will be assessed through patient surveys, which will include some open-ended items. The particular variables we will analyze include those on overall satisfaction with the medication abortion service (including whether they would use this mail-order medication abortion service again if they needed another abortion, and whether they would recommend the service to a friend), satisfaction with receiving the medications by mail, reasons for dissatisfaction (open ended questions), and perceptions about the wait time to receive the medications. We will also analyze the reasons why patients who decline participation in the study report not being interested in receiving the medications by mail, as indicated in close-ended and open-ended responses.

We plan to recruit for the main study a minimum sample of 440 participants and a maximum of 625 patients. With the addition of 25 patients in the pilot study, the target minimum number of patients recruited for the study is 465 and the maximum number is 650.

The sample size calculation for this study is based on two measures of acceptability: the proportion of patients who report they would use medication abortion again if they needed another abortion and the proportion who report they were “satisfied” or “very satisfied” with the medication abortion. For both power calculations, we assume 10% loss to follow up, 10% adjustment for clustering, a 5% non-inferiority margin, and a two-sided alpha of 0.05. Research with patients obtaining clinic-based medication abortion has estimated the proportion who would use medication abortion again as 89.7% (Teal, Dempsey-Fanning et al. 2007). Based on our assumptions, with a minimum sample of 440 patients, we will have a final analytic sample of approximately 400 patients, which gives us 79% power to assess this measure of acceptability; with a maximum sample of 625 recruited patients, we will have a final analytic sample of approximately 560 patients, which gives us 92% power.

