## 16.6 Sample Size

In addition to the 25 patients in the pilot study, we aim to recruit a minimum of 440 and a maximum of 625 patients for this study, across 15-20 sites. The sample size calculation for this study is based on a measure of acceptability: the proportion of patients who report they would use medication abortion again if they needed another abortion. Research with patients obtaining clinic-based MA has estimated that proportion as 89.7% (Teal, Dempsey-Fanning et al. 2007). We would like to determine if acceptability of medication abortion when receiving the medications by mail is no more than 5% lower than 89.7%. Assuming 10% loss to follow-up, with a minimum sample of 440 patients, we will have a final analytic sample of approximately 400 patients; with a sample of 625 recruited patients, we will have a final analytic sample of approximately 560 patients. With a 2-sided alpha of 0.05 and 10% adjustment for clustering, a final analytic sample size of approximately 400 gives us 79% power, and an analytic sample of 560 gives us 92% power to assess this measure of acceptability.

We aim to interview all the providers (or staff administrators) involved in medication abortion provision at the study sites, up to 50. This sample size will be determined by the number of providers/staff at the study sites.

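### The study is sized to rule out a 5-point shortfall, but the analyses it names do not test that limit, and the plan does not settle whether one or two acceptability measures decide

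*Combined protocol and SAP*

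**What the plan says.** **Acceptability.** The Protocol Synopsis (Primary Endpoint) defines the primary outcome by two proportions: those who "would use the mail-order service again if they needed another abortion, as well as the proportion who report they were" satisfied or very satisfied. Section 16.3 states that "The sample size calculation for this study is based on two measures of acceptability" and that, for both, "we assume 10% loss to follow up, 10% adjustment for clustering, a 5% non-inferiority margin, and a two-sided alpha of 0.05". The benchmarks are 89.7% for use-again and 88.4% for satisfaction. Section 16.6 says instead that "The sample size calculation for this study is based on a measure of acceptability", names use-again only, and gives the aim as showing that acceptability when "receiving the medications by mail is no more than 5% lower than 89.7" percent. The synopsis rationale for the number of subjects also uses that single measure and words the margin as percentage points.

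On analysis, Section 16.3 lists survey variables and power figures. The synopsis statistics entry names descriptive work with chi-square and t tests. Neither mentions a limit.

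**Effectiveness.** Section 16.4 compares the complete-abortion proportion "with published estimates (97.4%) (FDA 2016), using an exact binomial test". It then claims 98% to 100% power, at a two-sided alpha of 0.025, to determine that mail-order provision is "as effective as in-person dispensing, if effectiveness in the mail-order model is no lower than 92.4" percent, and adds: "A non-inferiority limit is defined as -5" percent.

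**Later SAP.** Section 16 says a detailed SAP will be written before the final analysis. None is in the supplied text.

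**The concern.** A power figure has meaning only alongside a rule for success. The plan gives power for excluding a 5-point deficit, but for acceptability it states no rule that would show the deficit has been excluded. Descriptive chi-square and t tests do not do so, and failing to find a significant shortfall from a benchmark is not the same as excluding a 5-point shortfall.

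Two further gaps affect how the results can be read. Whether one acceptability measure or both must succeed changes the power the study actually has. For effectiveness, a test against 97.4% and a margin at 92.4% are different questions; where they give different answers, a reader of the final report would not know which had been planned as decisive.

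**Working it through.** **Inputs.** From Sections 16.3, 16.4 and 16.6: benchmarks 89.7%, 88.4% and 97.4%; margin 5 points; two-sided alpha 0.05 for acceptability (0.025 per tail) and 0.025 for effectiveness (0.0125 per tail); 10% loss; 10% clustering adjustment.
- Limits: 89.7 − 5 = 84.7%; 88.4 − 5 = 83.4%; 97.4 − 5 = 92.4%. Only the last is printed.
- Analytic n: 440 × 0.9 = 396, about 400; 625 × 0.9 = 562.5, about 560.
- Effective n, taking the clustering adjustment as division by 1.1 (an assumption): 400/1.1 = 364; 560/1.1 = 509.

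**1. The plan's own power.** One-sample score test with the limit p0 as null and the benchmark p1 as truth:

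Power = Φ{[p1 − p0 − z√(p0(1−p0)/n)] / √(p1(1−p1)/n)}

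Use-again, n = 364: (0.05 − 1.960 × 0.01887)/0.01593 = 0.817, and Φ(0.817) = 79.3%.

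| Measure | Recomputed, n = 364 / 509 | Stated |
|---|---|---|
| Use-again, limit 84.7% | 79.3% / 91.8% | 79% / 92% |
| Satisfaction, limit 83.4% | 75.9% / 89.3% | 77% / 90% |
| Effectiveness, limit 92.4% (exact) | 98.4% / 99.9% | 98% to 100% |

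The stated powers are therefore sound for non-inferiority against these limits. They do not by themselves prove which null was meant: an exact test of 97.4% when the truth is 92.4% also has 98.3% / 99.8% power. The non-inferiority aim comes from the text.

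**2. Acceptability: why an explicit rule matters.** An exact non-inferiority rule takes the smallest x with P(X ≥ x | limit) ≤ 0.025.
- Use-again: at least 354/400 or 492/560. A true rate of 84.7% then passes 1.8% or 2.0% of the time.
- Illustration only, since the plan names no such test: suppose success meant not being significantly below 89.7%. An exact test rejects at 346/400 or fewer, or 487/560 or fewer. Then P(X ≥ 347 | n = 400, 0.847) = 14% and P(X ≥ 488 | n = 560, 0.847) = 6%, against an intended 2.5%.
- Example: 350/400 is 87.5%, exact 95% interval 83.9% to 90.6%. It is not significantly below 89.7% (two-sided p = 0.16 to 0.18, depending on the exact-test convention), yet it does not exclude 84.7%.

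**3. One measure or two.** From the plan's stated powers, if both must pass:
- Upper bound, the smaller of the two powers: 77% (n = 400), 90% (n = 560).
- If independent: 0.79 × 0.77 = 61%; 0.92 × 0.90 = 83%.

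**4. Effectiveness: the two possible rules.**

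| n | Excludes 92.4% (one-sided 0.0125) | Significantly below 97.4% | Both |
|---|---|---|---|
| 400 | 382 or more | 381 or fewer | none |
| 560 | 532 or more | 535 or fewer (equal tails) or 536 or fewer (minimum likelihood) | 532 to 535 or 536 |

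At every n from 400 to 560, under both conventions, a result that is not significantly below 97.4% also excludes 92.4%.

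Probability of the overlap at n = 560: 0.7% to 1.3% at a true 97.4%, 3% to 5% at 97%, 22% to 30% at 96%. For example, 534/560 has an exact 97.5% interval of 93.0% to 97.1%.

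**5. The power condition in Section 16.4.** Exact power to exclude 92.4%, using cut-offs 348/364 and 484/509:

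| True effectiveness | n = 364 | n = 509 |
|---|---|---|
| 97.4% | 98.4% | 99.9% |
| 96% | 71% | 88% |
| 95% | 35% | 52% |
| 92.4% | about 1% | about 1% |

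**The case against.** The strongest reply is that the intended rule is easy to infer. For acceptability the plan gives benchmark, margin, alpha and aim, which point to the usual confidence-limit rule. For effectiveness the test, the alpha, 92.4% and the margin stand within a few sentences of each other, and naming 97.4% as comparator does not strictly make it the null value. The promised SAP is the usual place to write such rules. Much of this stands: the gap may be one of drafting, and a later SAP may close it. But the plan does not state the inferred rule, and no inference settles whether one or two measures decide, because the sections disagree.

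A reader might infer more than the documents support:
- *That the effectiveness test could yield a false claim of non-inferiority.* It cannot at any analytic n from 400 to 560 (step 4). A result that is non-inferior yet significantly lower is also coherent; the defect is only that the plan does not say which finding governs.
- *That acceptability will be declared on non-significance against 89.7%.* The plan names no such test. The 14% and 6% show what an unwritten rule leaves open, not what the plan prescribes.
- *That passing either measure would suffice.* No section says so, and the synopsis joins the two measures.
- *That the power figures are wrong.* They reproduce to within about 1 point; only the condition attached to the effectiveness figure is misworded.

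**Conclusion.** The concern holds in this form and should be fixed. The study is sized for non-inferiority, but no named analysis tests 84.7% or 83.4%, and the one named effectiveness test is stated against 97.4% rather than 92.4%.

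The main consequences are for acceptability, the primary outcome. Its success rule is unwritten, and the basis of the decision differs between sections; requiring both measures would bring power down from 79% / 92% to at most 77% / 90%. For effectiveness, a secondary outcome, the consequence is narrower: an unresolved overlap of four or five success counts at n = 560, arising in about 1% of trials if the true rate is 97.4% but 22% to 30% if it is 96%, and never at n = 400. The effectiveness power claim is correct at a true 97.4% and wrong as conditioned.

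These results assume exact binomial calculations. The cut-offs and overlap probabilities use the undiscounted n. The power figures in steps 1 and 5 use the clustering discount, and the joint power uses the plan's stated powers.

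**What to change.** - **Section 16.3 and synopsis.** State that non-inferiority is concluded when the lower limit of the two-sided 95% interval exceeds 84.7% for use-again and 83.4% for satisfaction.
- **Synopsis, Sections 16.3 and 16.6.** Reconcile the one-measure and two-measure texts. Say either that one named measure decides, with the other supportive, or that both must pass. If both, give the joint power. Which option to take is a design choice for the investigators.
- **Section 16.4, test.** Set the null of the exact binomial test at 92.4%, so that success means the lower limit of the two-sided 97.5% interval is above 92.4%. Make any comparison with 97.4% descriptive.
- **Section 16.4, power sentence.** Reword to: 98–100% power to exclude effectiveness of 92.4% or lower if true effectiveness is 97.4%.
- **Planned SAP.** Carry the same rules into it.

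The cost is wording and minor analysis work, with no new data or patients. The one real cost arises if both measures must pass, because the power to be reported is then lower than the 79% and 92% now stated.
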